on days 1, 8, and 15 of a 28-day cycle, usually for multiple cycles. Following a 4-hour intravenous administration of RMD at 14 mg/m² on days 1, 8, and 15 of a 28-day cycle in patients with T-cell lymphomas, the terminal half-life (t1/2) was approximately 3 hours. No accumulation of RMD was observed after repeated dosing. Early clinical trials of RMD in CTCL patients revealed a potentially increased risk of QTc prolongation. As a result, the package insert for this drug indicates that it should not be given to a patient with a prolonged QTc. Side effects of RMD at the MTD include nausea, fatigue, vomiting, and anorexia. Common first cycle toxicities reported include bone marrow suppression and transient elevations of liver function tests [24-25, 32]. In clinical trials of RMD for T-cell lymphoma, bone marrow suppression has been associated with fatal and serious infections as well as reactivation of EBV and hepatitis B virus, RMD is predominantly metabolized by the cytochrome P450 enzyme CYP3A4. RMD is highly protein bound in plasma (92% to 94%) over the concentration range of 50 ng/mL to 1000 ng/mL with α 1-acid-glycoprotein (AAG) being the principal binding protein. Although there are no formal drug interaction studies for RMD, strong CYP3A4 inhibitors may increase plasma concentrations of RMD. RMD is also a substrate of the efflux transporter P-gp (ABSB1); hence drugs that inhibit P-gp may increase plasma concentrations of RMD. Finally, RMD competes with beta estradiol for binding to estrogen receptors, which inhibits their function (RMD Investigators Brochure v 10.0 May 2012).

HIV-infected	Fold increase	p value			
donor	over no drug control	vs. control			
1	4.8	0.03			
2	5.6	0.006			
3	14.0	0.0008			
4	3.0	0.0005			
5	5.9	0.02			
6	14.0	0.02			
7	5.2	0.00002			
8	2.8	0.01			
9	16.0	0.00003			
10	20.1	0.0003			
11	1.8	0.4			
12	5.8	0.005			
13	12.3	0.001			
	Avg = 8.6				
HIV-1 RNA levels were measured by Roche Taqman v2.0 at day 6 in culture supernatants of CD4+ memory T-cells from patients on suppressive ART. Intracellular HIV RNA was not measured.					

Table **2.2-1**: Induction of HIV-1 RNA *ex vivo*

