NOTE: This result must be available prior to the pre-entry visit.

- 4.1.7 The following laboratory values obtained within 21 to 0 days prior to study entry by any laboratory that has a CLIA certification or its equivalent.
 - Absolute neutrophil count (ANC) ≥1500 cells/mm³
 - Hemoglobin ≥12.0 g/dL for men and >11.0 g/dL for women
 - Platelet count ≥120,000/mm³
- 4.1.8 The following laboratory values obtained within 21 to 7 days prior to study entry by any laboratory that has a CLIA certification or its equivalent.
 - Creatinine clearance (CrCl) ≥60 mL/min
 - Potassium and magnesium within normal limits (see section 6.3.7 for details)
 - Aspartate aminotransferase (AST) (SGOT) <2.0 x upper limit of normal (ULN)
 - Alanine aminotransferase (ALT) (SGPT) <2.0 x ULN
 - Alkaline phosphatase <2.0 x ULN
 - Total bilirubin <2.5 x ULN
- 4.1.9 HCV antibody negative result within 90 to 50 days prior to study entry or, for study candidates who are HCV antibody positive (based on testing performed at any time prior to study entry), a negative HCV RNA result obtained within 90 to 50 days prior to study entry.
- 4.1.10 Negative HBsAg result obtained within 90 to 50 days prior to study entry or a positive HBsAb result at any time prior to study entry.
- 4.1.11 For females of reproductive potential, negative serum or urine pregnancy test (latter with a sensitivity of ≤25 mIU/mL) at the screening visit, pre-entry visit within 21 to 7 days prior to study entry, and at entry prior to romidepsin infusion, by any US laboratory that has a CLIA certification or its equivalent.

Note A: Reproductive potential is defined as:

- Girls who have reached menarche or
- Women who have had menses within the past 12 months and who do not have an FSH >40 IU/L or
- Women who have had menses within the past 24 consecutive months if an FSH measurement is not available
- Women who have not undergone surgical sterilization (eg, hysterectomy, or bilateral oophorectomy, or bilateral salpingectomy).

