 - Creatinine clearance (CrCl) ≥60 mL/min NOTE: A calculator for estimating the CrCl can be found at www.fstrf.org/ACTG/ccc.html
 - Potassium and magnesium within normal limits (see section 6.3.7 for details.)
 - Aspartate aminotransferase (AST) (SGOT) <2.0 x upper limit of normal (ULN)
 - Alanine aminotransferase (ALT) (SGPT) <2.0 x ULN
 - Alkaline phosphatase <2.0 x ULN
 - Total bilirubin <2.5 x ULN
- 4.3.7 HCV antibody negative result at screening (between 36 and 60 days prior to study entry) or, for study candidates who are HCV antibody positive (based on testing performed at any time prior to study entry), a negative HCV RNA result obtained at screening.
- 4.3.8 Negative HBsAg result obtained at screening (between 36 and 60 days prior to study entry) or a positive HBsAb result at any time prior to study entry.
- 4.3.9 For females of reproductive potential, negative urine pregnancy test (with a sensitivity of ≤25 mIU/mL) at screening (between 36 and 60 days prior to study entry), at pre-entry (between 3 and 14 days prior to study entry), and at entry prior to infusion, by any US laboratory that has a CLIA certification or its equivalent.

NOTE A: Reproductive potential is defined as:

- Girls who have reached menarche or
- Women who have had menses within the past 12 months and who do not have an FSH >40 IU/L or
- Women who have had menses within the past 24 consecutive months if an FSH measurement is not available
- Women who have not undergone surgical sterilization (eg, hysterectomy, or bilateral oophorectomy, or bilateral salpingectomy).
- NOTE B: Confirmation of the lack of reproductive potential is required. Written documentation or oral communication from a clinician or clinician's staff documented in source documents of one of the following must be provided: Physician report/letter, operative report or other source documentation in the patient record, discharge summary, laboratory report of azoospermia (required to document successful vasectomy), FSH measurement elevated into the menopausal range (as established by the reporting laboratory).
- NOTE C: If the female candidate cannot provide written proof of a male partner's vasectomy status, the oral report of her partner's status should be written into the source documents.

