Potassium and magnesium levels will be assessed 7 days prior to **the Steps 2**, **3**, **and 4** infusions. Blood potassium and magnesium values must be within normal limits. If the potassium and/or magnesium value is below the site's clinical laboratory's limit of normal, the participant should be supplemented as medically indicated, retested, and evaluated again within 3 days prior to the infusion. The repeated potassium and/or magnesium values must be within normal range for the site's limit of normal for the infusion to take place.

Given blood volume constraints in this study, sites should use pediatric volume tubes for checking potassium and magnesium levels whenever feasible.

Prior to the Steps 2, 3, and 4 infusions, if the potassium and magnesium levels are still out of range after retest, **c**onsultation with the core team is required before a decision about discontinuation is made ([contact]).

Blood Chemistries

All Cohorts

Electrolytes [sodium, potassium, chloride, phosphate, bicarbonate], calcium, magnesium, creatinine, blood urea nitrogen (BUN), and uric acid will be evaluated.

Calculated creatinine clearance estimated by the Cockcroft-Gault equation will be evaluated.

NOTE: A program for calculating creatinine clearance by the Cockcroft-Gault method is available on www.fstrf.org.

Urinalysis

Urinalysis with microscopic exam will be done at screening only.

Pregnancy Test

Pregnancy testing will be done per the SOE. For women of reproductive potential: Serum or urine β -HCG (urine test must have a sensitivity of \leq 25 mIU/mL).

For Cohort 4, only urine pregnancy testing is permitted.

Refer to section 7.2 for details on pregnancy and pregnancy outcome reporting.

Hepatitis Screen

HBsAg and HCV antibody testing will be done per the SOE. HCV RNA testing is required if HCV antibody positive. See sections 4.1.9, 4.1.10, 4.3.7, and 4.3.8 for details.

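### The hepatitis B entry criterion lets an undated positive HBsAb stand in for a negative screening HBsAg, so a candidate with a current positive HBsAg and a past positive HBsAb meets it

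*Protocol*

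**What the plan says.** For Cohorts 1 to 3, Protocol 4.1.10 accepts a "Negative HBsAg result obtained within 90 to 50 days prior to study entry or a positive HBsAb result at any time" before entry. For Cohort 4, 4.3.8 accepts a "Negative HBsAg result obtained at screening (between 36 and 60 days prior to study entry) or a positive HBsAb result at any time" before entry. In both, the first branch has a dated window and the second has none.

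The schedules of evaluations (6.1) mark a hepatitis screen at the screening visit in every cohort. Section 6.3.7 describes its content: "HBsAg and HCV antibody testing will be done per the SOE". It then refers back to the four hepatitis criteria for details. It does not name HBsAb as a scheduled test.

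The neighbouring hepatitis C criteria deal with an antibody-positive candidate differently. Section 4.1.9 then requires "a negative HCV RNA result obtained within 90 to 50 days prior to study entry", and 4.3.7 requires "a negative HCV RNA result obtained at screening".

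Section 2.2 says of the T-cell lymphoma trials of romidepsin that "bone marrow suppression has been associated with fatal and serious infections as well as reactivation of EBV and hepatitis B virus".

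**The concern.** The plan schedules a current HBsAg result and then allows an antibody record of any age to make that result irrelevant to eligibility. The same section requires a current virological result for hepatitis C when antibody is present, and the background section names hepatitis B reactivation as an observed harm of the drug class setting from which the agent comes. No reason is given for letting history replace the current hepatitis B result.

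What is at stake is first the participant who enters with a positive HBsAg. Cohort 4 participants are to receive up to four infusions, and the step criteria in 4.5 to 4.10 do not return to hepatitis B. It is also a matter of transparency. Someone admitted through the HBsAb branch has met the criterion, so the eligibility-violation table in SAP 7.2 would not show the case. The baseline table in SAP 7.4 lists HCV antibody but neither HBsAg nor HBsAb.

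**Working it through.** The plan gives no figure on this point, so the check is one of logic. Sections 4.1.10 and 4.3.8 have the same form: criterion met = (HBsAg negative in the screening window) OR (HBsAb positive at any past time).

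| Screening HBsAg | Past HBsAb | Criterion |
|---|---|---|
| negative | none positive | met |
| negative | positive | met |
| positive | none positive | not met |
| positive | positive | **met** |

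Only the last row is at issue. An HBsAg-positive candidate without a positive HBsAb fails.

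The next question is whether another rule excludes the last row:

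- **4.2.2 / 4.4.2** exclude a non-HIV infection that needed systemic therapy in the 30 days before entry. They would catch a candidate treated systemically for hepatitis B in that window, but not one who is HBsAg-positive without such treatment.
- **4.2.5 / 4.4.5** depend on the investigator judging an infection current and serious, and on incomplete therapy or clinical instability.
- **4.1.8 / 4.3.6** require AST and ALT below 2.0 times the upper limit of normal. They act on transaminases, so an HBsAg-positive candidate below that limit passes.
- **6.3.2** lists chronic hepatitis B as a diagnosis to record, not as an exclusion.
- **4.5 to 4.10** (Cohort 4, Steps 2 to 4) re-check HIV-1 RNA, pregnancy, potassium and magnesium, hematology, recent illness and vaccination. Hepatitis B is not among them.
- **8.1 and 8.2** contain no rule specific to hepatitis B.

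None of these turns on HBsAg. Some would catch some of the candidates in the last row, but none is certain to.

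Set beside the hepatitis C rule, the difference is plain. In 4.1.9 and 4.3.7 a positive antibody leads to a further current test that must be negative. In 4.1.10 and 4.3.8 a positive antibody, "or a positive HBsAb result at any time prior to study entry", ends the inquiry.

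Finally, whom can a change still affect? Section 5.1 describes the dosing of Cohorts 1 to 3 in the past tense (2.2 still writes of Cohort 3 enrolment in the future). The note in 1.1 refers to cells already available from some Cohort 4 participants. A change to Version 4.0 would therefore act mainly through 4.3.8, on whatever Cohort 4 enrolment remained.

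**The case against.** The strongest reply is that the gap is narrow and its consequence unquantified. It needs two findings together, a positive HBsAg now and a positive HBsAb in the past, and the partial backstops narrow the group further. That stands.

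The reactivation statement also has a specific setting. It concerns lymphoma trials and is tied to marrow suppression. Section 2.2 gives the lymphoma regimen as 14 mg/m² on days 1, 8 and 15 of a 28-day cycle, usually for several cycles. This study uses 0.5, 2 or 5 mg/m² once, or 5 mg/m² four times, with neutrophil and platelet floors at entry and before each later Cohort 4 infusion. Section 2.2 also reports no Grade 3 or 4 study-related events in six HIV-infected participants given three infusions of 5 mg/m². So the documents name the hazard but do not show its size here. That stands too.

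A reader might infer a probability that such a candidate is enrolled. This needs the frequency of the serology, which the documents do not give; any figure would only restate the assumed frequency. Using all 60 participants as the base would also be wrong for harm from the drug, since 4 × 3 = 12 of them receive placebo, and wrong for an amendment, since earlier cohorts are past.

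A reader might also infer that one flare would fail dose escalation. Criterion (b) in 9.4.1 counts events only up to Day 14, nothing shows that a flare would fall in that window or reach the required grade, and no cohort follows Cohort 4. The suspension in 9.5 is temporary and leads to review by an unblinded committee that looks again at relatedness.

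Two further replies have some force. The documents do not say that HCV antibody and HBsAb carry the same meaning, so the different structures are not in themselves a contradiction. And because 6.3.7 refers back to the criteria, a site could read it as allowing a documented HBsAb in place of a new HBsAg test. The second reply is itself a reason to make the text explicit.

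**Conclusion.** The point holds on the literal text for all four cohorts: a current positive HBsAg with any past positive HBsAb satisfies 4.1.10 and 4.3.8, and no other criterion in the protocol acts on HBsAg. It does not hold that HBsAg-positive candidates in general can enter, since those without a positive HBsAb fail.

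No size can be put on it. The frequency of the combination and the reactivation risk at the study doses are both absent from the documents, and the claim rests on neither. It rests on reading the criterion as a plain OR, and on there being no overriding rule in the manual of procedures, which is not one of the two documents. This is a small wording gap with a named hazard behind it. It is worth closing because the deciding result is already scheduled, not because a large effect on the trial has been shown.

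**What to change.** Reconcile 4.1.10 and 4.3.8 with the hepatitis screen in 6.3.7, the reactivation statement in 2.2 and the hepatitis C criteria in 4.1.9 and 4.3.7, so that an undated HBsAb record does not override the HBsAg result already scheduled at screening. State explicitly what a positive screening HBsAg means for eligibility when a past positive HBsAb exists, and whether HBsAg must be drawn in every candidate. In practice the edit that matters is to 4.3.8, for remaining Cohort 4 enrolment.

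The cost is a short amendment to the criteria, possibly a very small number of candidates excluded, and an HBsAg test at any site that had been relying on documented HBsAb alone. Elsewhere no new test is needed.

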4.11.2 Protocol Activation

Following initial registration to the protocol, sites must complete the Protocol Activation Checklist found on the ACTG Member website. The completed checklist must be approved before screening of study candidates can begin.

4.11.3 Randomization/Participant Registration

At entry, candidates will be enrolled according to standard ACTG DMC procedures. For candidates from whom informed consent has been obtained, but who are deemed ineligible or who do not enroll into the initial protocol step, an ACTG Screening Failure Results form must be completed and keyed into the database.

4.12 Coenrollment Guidelines

Sites are encouraged to coenroll participants in A5128, "Plan for Obtaining Informed Consent to Use Stored Human Biological Materials (HBM) for Currently Unspecified Analyses." Coenrollment in A5128 does not require permission from the protocol chairs of either study. Because of blood volume limitations in A5315, sites must NOT collect a separate blood sample during the A5315 study follow up period from participants who coenroll in A5128.

For specific questions and approval for coenrollment into other studies, sites should check the PSWP or contact the core team via e-mail ([contact]).

5.0 STUDY TREATMENT

Study treatment is defined as Romidepsin (RMD) or Placebo for RMD. ART is required but it will not be provided by the study.

5.1 Regimens, Administration, and Duration

At entry, participants will be randomized (4:1) to receive blinded RMD or Placebo for RMD. The first fifteen study participants enrolled in Cohort 1 and received one dose of blinded RMD or Placebo for RMD by intravenous (IV) infusion over 4 hours on Day 0. Additional participants are enrolled, approximately 15 per cohort, into different cohorts as these are opened to accrual.

Participants in Cohorts 2 and 3 received one dose of blinded RMD, at increased dosages, or placebo for RMD by IV infusion over 4 hours on Day 0. Participants in Cohort 4 will receive a dose of blinded RMD or placebo for RMD by IV infusion over 4

hours on Days 0, 14, 28, and 42, for a total of four doses. Each Cohort 4 participant will receive four doses of either RMD or placebo for RMD.

After Cohort 1, Cohorts 2 and 3 were opened sequentially, based on safety outcomes as defined in section 9.0. The decisions to open these two subsequent cohorts were made after two separate reviews of available safety data by the A5315 core team and SMC.

Body Surface Area (BSA) Calculation

The dose of RMD to be administered will be calculated based on body surface area (BSA) expressed in square meters (m²), which will be determined by weight and height measurement. Measured height and weight obtained during the complete physical exam at pre-entry is to be used for calculating the BSA for the first infusion. For Cohort 4, the weight **and height recorded at the first pre-entry visit** will be used for calculating the BSA for **Step 1**. Weight recorded at Days 7, 21, and 35 and height recorded at the first pre-entry visit will be used for Cohort 4 Steps 2, 3, and 4, respectively.

The BSA should be calculated using the BSA calculator available on the FSTRF portal.

BSA (m²) = ([Height (cm) x Weight (kg)] / 3600)^{1/2}

5.1.1 Cohort 1

Upon randomization, the participant PID and SID will be provided to the site clinic for the clinic to send a prescription to the pharmacy.

o Arm 1A (RMD)

RMD intravenously (IV) over 4-hours starting at Hour 0 on Day 0. The mg dose and corresponding volume of RMD to be added to 500 mL 0.9% Sodium Chloride for Injection, USP IV bag for infusion is based on participant's BSA per Table 5.1.1-1.

OR

o Arm 1B (Placebo for Romidepsin)

0.9% Sodium Chloride (NaCl) for Injection USP, IV over 4 hours starting at Hour 0 on Day 0. The volume of 0.9% NaCl for injection, USP to be added to 500 mL 0.9% Sodium Chloride for Injection, USP IV bag for infusion is based on participant's BSA per Table **5.1.1-1**.

		Arm 1A: RMD	Arm 1B: Placebo for RMD
	Dose of	Volume of RMD to add to	Volume of 0.9% NaCl for
BSA Range	RMD	500 mL 0.9% Sodium	Injection, USP to add to 500 mL
	(mg)	Chloride for Injection,	0.9% Sodium Chloride for
	_	USP IV Bag in Arm 1A	Injection USP IV Bag in Arm 1B
1.35 - 1.74	0.75 mg	0.15 mL	0.15 mL
1.75 - 2.24	1 mg	0.2 mL	0.2mL
2.25 - 2.54	1.25 mg	0.25 mL	0.25 mL
2.55 - 3	1.5 mg	0.3 mL	0.3 mL

Table **5.1.1-1**: RMD and Placebo for RMD Dosing at 0.5 mg/m² Dose Level in Cohort 1

5.1.2 Cohort 2

Upon randomization, the participant PID and SID will be provided to the site clinic for the clinic to send a prescription to the pharmacy.

o Arm 2A (RMD)

RMD intravenously (IV) over 4-hours starting at Hour 0 on Day 0. The mg dose and corresponding volume of RMD to be added to 500 mL 0.9% Sodium Chloride for Injection, USP IV bag for infusion is based on participant's BSA per Table **5.1.2-1**.

OR

• Arm 2B (Placebo for RMD)

0.9% Sodium Chloride for Injection, USP IV over 4 hours starting at Hour 0 on Day 0. The volume of 0.9% NaCl for injection, USP to be added to 500 mL 0.9% Sodium Chloride for Injection, USP IV bag for infusion is based on participant's BSA per Table **5.1.2-1**.

Table 5.1.2-1: RMD and Placebo for RMD Dosing at 2 mg/m² Dose Level in Cohort 2

		Arm 2A: RMD	Arm 2B: Placebo for RMD
	Dose of	Volume of RMD to add to	Volume of 0.9% NaCl for
BSA Range	RMD	500 mL 0.9% Sodium	Injection, USP to add to 500 mL
	(mg)	Chloride for Injection USP	0.9% Sodium Chloride for
	_	IV Bag in Arm 2A	Injection USP IV Bag in Arm 2B
1.35 - 1.74	3 mg	0.6 mL	0.6 mL
1.75 - 2.24	4 mg	0.8 mL	0.8 mL
2.25 - 2.54	5 mg	1 mL	1 mL
2.55 - 3	6 mg	1.2 mL	1.2 mL

5.1.3 Cohort 3

Upon randomization, the participant PID and SID will be provided to the site clinic for the clinic to send a prescription to the pharmacy.

o Arm 3A (RMD)

RMD intravenously (IV) over 4-hours starting at Hour 0 on Day 0. The mg dose and corresponding volume of RMD to be added to 500 mL 0.9% Sodium Chloride for Injection, USP IV bag for infusion is based on participant's BSA per Table 5.1.3-1.

OR

• Arm 3B (Placebo for RMD)

0.9% Sodium Chloride for Injection, USP IV over 4 hours starting at Hour 0 on Day 0. The volume of 0.9% NaCl for injection, USP to be added to 500 mL 0.9% Sodium Chloride for Injection, USP IV bag for infusion is based on participant's BSA per Table **5.1.3-1**.

Table 5.1.3-1: RMD and Placebo for RMD Dosing at 5 mg/m² Dose Level in Cohort 3

		 	
		Arm 3A:	Arm 3B:
		RMD	Placebo for RMD
BSA Range	Dose of	Volume of RMD to add	Volume of 0.9% NaCl for
DSA Range	RMD	to 500 mL 0.9% Sodium	Injection, USP to add to 500 mL
	(mg)	Chloride for Injection,	0.9% Sodium Chloride for
		USP IV Bag in Arm 3A	Injection, USP IV Bag in Arm 3B
1.35 - 1.74	8 mg	1.6 mL	1.6 mL
1.75 - 2.24	10 mg	2 mL	2L
2.25 - 2.54	12 mg	2.4 mL	2.4 mL
2.55 - 3	14 mg	2.8 mL	2.8 mL

5.1.4 Cohort 4

Upon randomization **to each step**, the participant's PID and SID will be provided to the site clinic for the clinic to send a prescription to the pharmacy. A new prescription that includes the participant's most recent BSA must be provided to the pharmacy at least 5 days prior to each subsequent infusion.

Arm 4A (RMD)

RMD intravenously (IV) over 4 hours starting at Hour 0 on Day 0 and at Hour 0 on Days 14, 28, and 42, for a total of four doses. The mg dose and corresponding volume of RMD to be added to 500 mL **0.9%** Sodium Chloride for Injection, USP IV bag for infusion is based on the participant's BSA per Table 5.1.4-1.

Arm 4B (Placebo for RMD)

0.9% Sodium Chloride for Injection, USP IV over 4 hours starting at Hour 0 on Day 0 and at Hour 0 on Days 14, 28, and 42, for a total of four doses. The volume of 0.9% NaCl for injection, USP, to be added to 500 mL **0.9%** Sodium Chloride for Injection, USP IV bag for infusion is based on the participant's BSA per Table **5.1.4-1**.

Table 5.1.4-1:	RMD and Placebo for	or RMD Dosing at 5 mg/m ²	Dose Level in Cohort 4

		Arm 4A:	Arm 4B:
		RMD	Placebo for RMD
BSA	Dose of	Volume of RMD to add	Volume of 0.9% NaCl for
Range	RMD	to 500 mL 0.9% Sodium	Injection, USP to add to 500 mL
	(mg)	Chloride for Injection,	0.9% Sodium Chloride for
	_	USP IV Bag in Arm 4A	Injection, USP IV Bag in Arm 4 B
1.35 - 1.74	8 mg	1.6 mL	1.6 mL
1.75 - 2.24	10 mg	2 mL	2 mL
2.25 - 2.54	12 mg	2.4 mL	2.4 mL
2.55 - 3	14 mg	2.8 mL	2.8 mL

- 5.2 Study Product Formulation and Preparation
 - 5.2.1 Study Product Formulation

RMD

RMD (Istodax®) is supplied as a kit in a single carton that includes a sterile, lyophilized powder in a single-use vial containing 10 mg of RMD and 20 mg of the bulking agent, povidone, USP. In addition, each kit includes 1 sterile vial containing 2 mL (deliverable volume) of the Diluent composed of 80% propylene glycol, USP, and 20% dehydrated alcohol, USP. RMD for injection vial and diluent vial in a single carton must be stored at 20° to 25°C, excursions permitted between 15° to 30°C. (See USP Controlled Room Temperature.)

Placebo for RMD

0.9% Sodium Chloride for Injection, USP in single use vial will be used as the Placebo for RMD and must be stored as directed by the manufacturer.

- 5.2.2 Study Product Preparation and IV Administration
 - 5.2.2.1 RMD Preparation

One vial of RMD 10 mg and one vial containing 2 mL of diluent included in the RMD kit in a single carton will be needed to prepare RMD dose.

RMD should be handled in a manner consistent with recommended safe procedures for handling cytotoxic drugs. Caution should be exercised in handling RMD. The use of gloves and gown is recommended. If RMD

comes in contact with the skin or mucosa, immediately wash thoroughly with soap and water.

The pharmacist will prepare RMD dose in a biological safety cabinet or an isolator using aseptic technique.

RMD must be reconstituted with the supplied Diluent and further diluted with 0.9% Sodium Chloride for Injection, USP before intravenous infusion.

Using aseptic technique, reconstitute RMD 10 mg vial with supplied Diluent. Using a 3 mL or 5 ml size syringe, withdraw 2 mL from the supplied Diluent vial and slowly inject it into the 10 mg RMD for injection vial.

Swirl the contents of the RMD vial until there are no visible particles in the resulting solution. The reconstituted solution will contain RMD 5 mg/mL.

The reconstituted RMD solution in the vial is chemically stable for 8 hours at room temperature.

Withdraw the specified amount of participant's dose of RMD in mL from the reconstituted RMD vial. Refer to the RMD and Placebo for RMD dosing Tables for the specified amount of participant's dose for each dosing cohort and BSA for each participant.

If the participant's specified dose volume of RMD is less than 1 mL, then use a 1 mL size syringe to withdraw the participant's dose from the reconstituted RMD vial.

If the participant's specified dose volume of RMD is equal to 1 mL, then use a 3 mL size syringe to withdraw the participant's dose volume (mL) from the reconstituted RMD vial.

If the participant's dose volume of RMD is greater than 1 mL and less than 2 mL, then use a 3 mL size syringe to withdraw 1 mL of reconstituted RMD solution and a 1 mL size syringe to withdraw less than 1 mL volume of reconstituted RMD solution from the vial.

If the participant's specified dose volume of RMD is equal to 2 mL, then use a 3 mL size syringe to withdraw the participant's dose volume (mL) from the reconstituted RMD vial.

If the participant's specified dose volume of RMD is greater than 2 mL and less than 3 mL, then use a 3 mL size syringe to withdraw 2 mL of

reconstituted RMD solution and a 1 mL size syringe to withdraw less than 1 mL volume of reconstituted RMD solution from the vial.

Inject the participant's specified RMD dose volume (mL) into a 500 mL 0.9% Sodium Chloride for injection, USP IV bag for infusion.

Label the participant's prepared blinded RMD study drug for infusion in 500 mL 0.9% NaCl IV bag as *"Romidepsin ____mg or Placebo for Romidepsin"* study product.

The RMD mg amount to state on the blinded label is the participant's specified RMD total dose in mg that was withdrawn into the syringe(s) and injected into a 500 mL 0.9% NaCl injection, USP IV bag for infusion.

The solution for infusion prepared as above is stable for up to 24 hours when stored at room temperature. The infusion must be completed within 24 hours from the time the RMD vial is reconstituted to the end of infusion of the prepared IV solution.

Discard any unused RMD solution according to proper handling and disposal procedures for cytotoxic drugs.

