5.3.2 Study Product Acquisition/Distribution

RMD (Istodax®) will be available through the NIAID Clinical Research Products Management Center (CRPMC). The ACTG site pharmacist can obtain the study product for this protocol by following the instructions in the manual, *Pharmacy Guidelines and Instructions for DAIDS Clinical Trials Networks,* in the section entitled Study Product Control.

After the pre-entry visit is completed, the site investigator must provide the site pharmacist with the participant's PID number and BSA. The site pharmacist must include the PID number and BSA when ordering study product from the CRPMC.

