Record and key within 2 business days, the RMD/placebo infusion, including dose administered, whether administration was temporarily halted for any reason, duration of infusion, and whether the full dose was administered. If the infusion is temporarily halted, the schedule of evaluations should resume following completion of the RMD/placebo infusion (referred to as Hour 4, regardless of whether the actual time from infusion start to completion took more time than 4 hours). See sections 6.2.3 and 6.3.11. Record any unscheduled discontinuation of RMD or placebo for RMD.

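### Protocol 5.2.2.1 allots one 10 mg (2 mL) romidepsin vial per dose, but the 12 mg and 14 mg doses in Cohorts 3 and 4 each need two kits

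*Protocol*

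**What the plan says.** Protocol 5.2.1 describes the product as a kit: "lyophilized powder in a single-use vial containing 10 mg of RMD", packed with one diluent vial whose deliverable volume is 2 mL. Section 5.2.2.1 gives the materials for one dose as "One vial of RMD 10 mg and one vial containing 2 mL of diluent included in the RMD kit". It then states: "The reconstituted solution will contain RMD 5 mg/mL".

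The dosing tables for the 5 mg/m² level (5.1.3-1 for Cohort 3 and 5.1.4-1 for Cohort 4) have the same four bands:

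| BSA (m²) | Dose | Volume |
|---|---|---|
| 1.35–1.74 | 8 mg | 1.6 mL |
| 1.75–2.24 | 10 mg | 2 mL |
| 2.25–2.54 | 12 mg | 2.4 mL |
| 2.55–3 | 14 mg | 2.8 mL |

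Section 5.2.2.1 then sets syringe steps by volume. The last applies when the "specified dose volume of RMD is greater than 2 mL and less than 3 mL": 2 mL is drawn with one syringe and the remainder with another, both from one vial (singular). The pharmacist must then inject the "specified RMD dose volume (mL) into a 500 mL 0.9% Sodium Chloride for injection" bag.

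The protocol text supplied does not mention a second vial or kit anywhere. On ordering, section 5.3.2 says only: "The site pharmacist must include the PID number and BSA when ordering study product from the CRPMC".

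**The concern.** Section 5.2.2.1 is the operative instruction for preparing the drug. For the two upper BSA bands at 5 mg/m² it asks for more solution than its stated materials contain. The authors foresaw volumes above 2 mL, since they wrote a step for them, but the vial count was not adjusted.

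What is at stake is delivery of the assigned dose:

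- With only one kit to hand, the site must delay the infusion or give less than the assigned dose. If sites resolved this differently, delivered dose could vary between them.
- Each cohort has about 12 participants on RMD, so each person's exposure matters.
- Cohort 3 safety at 5 mg/m² determines whether Cohort 4 opens (Protocol 9.1).
- The as-treated efficacy set is defined by completed infusions (Protocol 9.6, SAP 6.3). A bag made from one vial and infused to the end could still count as a completed treatment.

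No harm to blinding or labelling is claimed.

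**Working it through.** **Inputs.** Vial content 10 mg and diluent 2 mL (Protocol 5.2.1); one vial of each per dose, 5 mg/mL after reconstitution (5.2.2.1); doses and volumes by BSA band (Tables 5.1.1-1, 5.1.2-1, 5.1.3-1, 5.1.4-1); BSA = √(height in cm × weight in kg / 3600) (5.1).

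**1. Reproduce the stated concentration and table volumes.**
- 10 mg / 2 mL = 5 mg/mL, as stated.
- Volume = dose / 5: 8/5 = 1.6, 10/5 = 2.0, 12/5 = 2.4 and 14/5 = 2.8 mL. These match the tables, as do the volumes for Cohorts 1 and 2. The tables are correct.

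**2. Kits per dose = dose / 10 mg, rounded up.**
- Cohort 1 (largest dose 1.5 mg, 0.3 mL) and Cohort 2 (largest 6 mg, 1.2 mL): one kit.
- Cohorts 3 and 4, 8 mg and 10 mg: one kit.
- 12 mg: 12/10 = 1.2, so two kits. One vial is short by 2 mg (0.4 mL), or 2/12 = 16.7% of the dose.
- 14 mg: 14/10 = 1.4, so two kits. One vial is short by 4 mg (0.8 mL), or 4/14 = 28.6%.

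The one-vial statement holds for every tabulated dose of 10 mg or less and fails for these two. The diluent volume is given as deliverable, and no overfill is stated that could supply the extra 0.4 or 0.8 mL.

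**3. Dose delivered if a single vial were used.**

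| BSA band (m²) | One vial, 10 mg (mg/m²) | Tabulated dose (mg/m²) | Fraction of dose |
|---|---|---|---|
| 2.25–2.54 | 10/2.54 = 3.94 to 10/2.25 = 4.44 | 12/2.54 = 4.72 to 12/2.25 = 5.33 | 10/12 = 83% |
| 2.55–3 | 10/3 = 3.33 to 10/2.55 = 3.92 | 14/3 = 4.67 to 14/2.55 = 5.49 | 10/14 = 71% |

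For comparison, correct banding already gives 10/2.24 = 4.46 mg/m² at BSA 2.24. At BSA 2.25 the one-vial dose (4.44) is almost the same. At BSA 3 it is one third below the 5 mg/m² target.

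**4. Supply for a Cohort 4 course.** 4 infusions × 2 kits = 8 kits, rather than 4, if BSA stays in these bands at all four infusions.

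**5. Who reaches these bands.** Weight = 3600 × BSA² / height. The heights are assumed, because the documents give no height or weight distribution.

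| Height (cm) | Weight at BSA 2.25 (kg) | Weight at BSA 2.55 (kg) |
|---|---|---|
| 170 | 18225/170 = 107 | 23409/170 = 138 |
| 180 | 18225/180 = 101 | 23409/180 = 130 |
| 190 | 18225/190 = 96 | 23409/190 = 123 |

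The eligibility criteria set no upper limit on BSA, and the tables extend to 3 m².

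**The case against.** The strongest reply is that the error reveals itself. Nobody can draw 2.4 mL from 2 mL, and the protocol fixes the required result: the tabulated dose, injected in full. Opening a second kit satisfies everything except the one-vial sentence, whereas stopping at 10 mg breaks the table and the injection instruction. The one-vial doses above are therefore a worst case that the protocol does not permit, not the expected outcome. That is right, and it limits the likely harm.

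Several safeguards also count:

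- BSA goes with each product order (5.3.2), perhaps so that the shipment can be sized. That section also points to a separate pharmacy manual, not available here, which may cover kit numbers.
- In Cohort 4 a new prescription with current BSA is due at least 5 days before each later infusion (5.1.4).
- The bag label must show the milligrams actually withdrawn (5.2.2.1).
- Section 6.3.4 records the dose given and "whether the full dose was administered", and SAP 7.6 lists incomplete treatments with the percentage infused.

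These make a shortfall less likely or easier to detect. None of them states a kit count in the documents, and none makes the one-vial rule correct.

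It is also fair to say that the volume tiers mainly govern syringe size, since the placebo section repeats them for saline. That explains how the slip arose. But the RMD step still names one vial as the source of more than 2 mL. Finally, few people may be affected, any shortfall would be an under-dose, and the randomization, power and analysis methods do not depend on the sentence. All of that stands, and it bears on how serious the error is, not on whether it is one.

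**Conclusion.** The concern holds. Section 5.2.2.1 is wrong for the 12 mg and 14 mg doses: each needs two kits, and the withdrawal step cannot be carried out from one vial. Only the RMD arms of Cohorts 3 and 4 at BSA 2.25 m² or more are affected. Cohorts 1 and 2 and all doses of 10 mg or less are sound, as are the tabulated dose and volume pairs.

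The worst case is delivery of 83% or 71% of the assigned dose (3.33–4.44 mg/m² across the two bands). That assumes a site stopped at one vial, which is possible but not the likeliest outcome. The kit count is certain from the protocol's own numbers, given no usable overfill. The effect on actual dosing is not certain, and the number of participants concerned is unknown and may be zero. It should be corrected because it is a working dose-preparation rule that fails for doses the protocol itself prescribes.

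**What to change.** - In 5.2.2.1, state that a dose above 10 mg (volume above 2 mL) requires two kits, each reconstituted with its own 2 mL of diluent.
- Reword the step for volumes between 2 and 3 mL so that 2 mL comes from the first vial and the remainder from the second.
- In 5.3.2, give the same kit count for ordering: two per infusion at BSA 2.25 m² or more at the 5 mg/m² level.
- Check past dosing. Section 5.1 reports that "Participants in Cohorts 2 and 3 received one dose of blinded RMD", and the note in section 1.1 shows that some Cohort 4 participants have already been sampled. For RMD-arm participants with BSA 2.25 m² or more in Cohort 3, and in Cohort 4 to date, compare the recorded administered dose with the pharmacy preparation records. Someone with access to treatment assignments should do this, so that the study team stays blinded.

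The cost is a short clarification memo and a record check confined to those participants. No change to the design or the analysis plan is needed.
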